mmHg). All these improvements must be sustained for at least 48 hours. Percentage of Participants at Each Clinical Status at Day 14 and Day 28 assessed by using the ordinal NIAID 8- point Clinical Progression Outcomes scale: 1) Death; 2) Hospitalized, on invasive mechanical ventilation extracorporeal membrane oxygenation *(ECMO)*; 3) Hospitalized, on non-invasive ventilation or high flow oxygen devices; 4) Hospitalized, requiring supplemental oxygen; 5) Hospitalized, not requiring supplemental oxygen - requiring ongoing medical care (COVID-19 related or otherwise); 6) Hospitalized, not requiring supplemental oxygen - no longer requires ongoing medical care; 7) Not hospitalized, limitation on activities and/or requiring home oxygen; 8) Not hospitalized, no limitations on activities To evaluate preliminary Difference in proportions of patients with evidence of anti-viral conversion of positive RT-PCR to negative RTactivity of CX-4945 as PCR as assessed at Day 1, Day 8, Day 14 and Day compared to the control 28. arm. Changes in chest imaging from Screening to Day 5 or 14 (if applicable) as defined by: Number of quadrants/ pulmonary lobes affected Change in number and/or size of COVID-19 pulmonary lesions (ground-glass opacity, consolidation, mix pattern) assessed by chest CT/X-ray

CONFIDENTIAL Page 11 of 66

[figure not shown]
	To evaluate the Clinical Benefit of Silmitasertib (CX-4945) relative to the control arm in patients with Severe COVID-19.	 Days of hospitalization from randomization through Day 28. Days of supplemental oxygen (if applicable) from randomization through Day 28. All-cause mortality status - the number of deaths occurred in each treatment group from randomization through Day 60. Days of non-invasive ventilation/high flow oxygen (if applicable) from randomization through Day 28. Days of invasive mechanical ventilation/ECMO (if applicable) from randomization through Day 28. Number of patients returned to room air after randomization through Day 14 or Day 28. Change in pulse oxygen saturation (SpO2) from randomization to Day 4, 8, 11, 14 and 28. Number of documented venous thromboembolism (VTE), arterial thrombosis (stroke, myocardial infarction, other) and microthrombosis events from randomization through Day 28. Changes in EQ-D5-5L (used as an indicator of symptom improvement) from randomization to Day 8, 14 and 28.

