3. OBJECTIVES AND ENDPOINTS

Primary Objective	Primary Endpoint
To assess safety and tolerability of CX-4945 administered orally twice daily to patients with severe COVID-19	• Adverse Events experienced by patients from randomization to Day 60 (including vital signs, physical findings, clinical laboratory, and ECG results) as characterized by type, frequency, severity (as graded by Common Terminology Criteria for Adverse Events (CTCAE version 5.0), timing, seriousness, and relationship to study therapy.
Secondary Objectives	Secondary Endpoints
• To compare time to clinical recovery in the CX-4945 treatment group evaluated from randomization through Day 28 as compared to the control arm.	• Number of days from randomization to discharge, or alleviation of cough (defined as mild or absent in a patient reported scale of 0=absent, 1=mild, 2=moderate, and 3=severe). Improvement must be sustained for at least 48 hours.
	• Number of days from randomization to normalization of fever (defined as <36.6°C from axillary site, or < 37.2°C from oral site or < 37.8°C from rectal or tympanic site), normalization of respiratory rate (< 24 bpm while breathing room air), resolution of hypoxia (defined as SpO2 ≥ 93% in room air or P/F ≥ 300 mmHg). All these improvements must be sustained for at least 48 hours.
	 Number of days from randomization to the first day on which the subject satisfies one of the following three categories from the ordinal NIAID 8-point Clinical Progression Outcomes scale collected daily from randomization through Day 28:
	Hospitalized, not requiring supplemental oxygen - no longer requires ongoing medical care;
	 Not hospitalized, limitation on activities and/or requiring home oxygen;
	Not hospitalized, no limitations on activities.
To compare changes in clinical status of patients enrolled to CX-4945 treatment arm as	Difference in percentage of subjects with clinical recovery compared at Day 14 and Day 28. Clinical recovery is defined as:

CONFIDENTIAL Page 22 of 66

s. ty	ite, or < 37.2°C from oral site or < 37.8°C from rectal or ympanic site), normalization of respiratory rate (< 24 bpm
a	while breathing room air), resolution of hypoxia (defined as $SpO2 \ge 93\%$ in room air or $P/F \ge 300$ mmHg). All these mprovements must be sustained for at least 48 hours.
Day	centage of participants at each clinical status at Day 14 and 28 assessed by using the ordinal NIAID 8- point Clinical gression Outcomes scale:
1) L	Death;

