	Hospitalized, on invasive mechanical ventilation or acorporeal membrane oxygenation (ECMO);
· · · · · · · · · · · · · · · · · · ·	Hospitalized, on non-invasive ventilation or high flow gen devices;
4) H	Hospitalized, requiring supplemental oxygen;
	Hospitalized, not requiring supplemental oxygen - requiring oing medical care (COVID-19 related or otherwise);
· ·	Hospitalized, not requiring supplemental oxygen - no longer uires ongoing medical care;
	Not hospitalized, limitation on activities and/or requiring ne oxygen;
8) N	ot hospitalized, no limitations on activities
evidence of anti-viral activity of CX-4945 as compared to the Day	Gerence in proportions of patients with conversion of tive RT-PCR to negative RT-PCR as assessed at Day 1, 8, Day 14 and Day 28
	inges in chest imaging from Screening (Day 0)to Day 5 or 14 (if applicable) as defined by:
0]	Number of quadrants/ pulmonary lobes affected

CONFIDENTIAL Page 23 of 66

	 Change in number and/or size of COVID-19 pulmonary lesions (ground-glass opacity, consolidation, mix pattern) assessed by chest CT/X-ray
To evaluate the Clinical Benefit of Silmitasertib (CX-4945) relative to the control arm in patients with Severe COVID-19.	 Days of hospitalization from randomization through Day 28. Days of supplemental oxygen (if applicable) from randomization through Day 28. All-cause mortality status: the number of deaths occurred in each treatment group from randomization through Day 60. Days of non-invasive ventilation/high flow oxygen (if applicable) from randomization through Day 28. Days of invasive mechanical ventilation/ECMO (if applicable) from randomization through Day 28. Number of patients returned to room air after randomization through Day 14 or Day 28. Change in pulse oxygen saturation (SpO2) from randomization to Day 4, 8, 11, 14 and 28. Number of documented venous thromboembolism (VTE), arterial thrombosis (stroke, myocardial infarction, other) and microthrombosis events from randomization through Day 28. Changes in EQ-D5-5L (used as an indicator of symptom improvement) from randomization to Day 8, 14 and 28.
To evaluate changes in inflammatory markers	 Changes in plasma IL-6 level from randomization to Day 4, 8, 11, and 14 Changes in CRP, LDH, CPK, ferritin, D-dimer from randomization to Day 4, 8, 11, and 14

CONFIDENTIAL Page 24 of 66

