5. STUDY POPULATION

This study will enroll up to approximately 40 patients with severe Coronavirus Disease 2019 (COVID-19). All study participants will be identified from the currently hospitalized patients. SOC/Best supportive care alone or in combination with CX-4945 will be given to study subjects.

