8.2.2.3. COVID-19 8-Point Clinical Progression Outcomes Scale

Progression is assessed on COVID-19 8-point ordinal scale collected daily from randomization through Day 28, regardless of discharge or treatment discontinuation status, to adequately capture relevant COVID19 outcomes. Remote data collection methods, such as electronic data collection, phone, and telehealth assessments can be used after patient discharge from the hospital through Day 28 (see **Section 1.3**). The ordinal scale of patient health status ranges from: 1) Death; 2) Hospitalized, on invasive mechanical ventilation or extracorporeal membrane oxygenation (ECMO); 3) Hospitalized, on non-invasive ventilation or high flow oxygen devices; 4) Hospitalized, requiring supplemental oxygen; 5) Hospitalized, not requiring supplemental oxygen - requiring ongoing medical care (COVID-19 related or otherwise); 6) Hospitalized, not requiring supplemental oxygen - no longer requires ongoing medical care; 7) Not hospitalized, limitation on activities and/or requiring home oxygen; 8) Not hospitalized, no limitations on activities.

8.2.2.4. Pulse Oxygen Saturation (SpO2):

Measuring the amount of oxygen-carrying hemoglobin in the blood relative to the amount of hemoglobin not carrying oxygen will be done at the time points described in the Schedule of Activities (see Section 1.3).

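### The protocol gives no rule for deaths in the Day 28 hospital-day and support-day counts, so early deaths can read as a shorter stay

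*Combined protocol and SAP*

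**What the plan says.** Section 3, under the objective on clinical benefit relative to control, lists four day counts: "Days of hospitalization from randomization through Day 28", "Days of supplemental oxygen (if applicable) from randomization through Day 28", "Days of non-invasive ventilation/high flow oxygen (if applicable) from randomization through Day 28" and "Days of invasive mechanical ventilation/ECMO (if applicable) from randomization through Day 28". The synopsis (Section 1.1) repeats them. None comes with a value, rank, censoring rule or competing-event rule for a patient who dies.

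Everyone starts in hospital: "All study participants will be identified from the currently hospitalized patients" (Section 5). Efficacy is analysed in all randomized patients (Section 9.7.1.1), so patients who die stay in the counts. Continuous endpoints go to ANCOVA, or to a non-parametric or rank-ANCOVA method if normality fails (Section 9.8.4.1). Section 9.8.4 speaks instead of descriptive summaries without inference. Missing efficacy data are to be multiply imputed (Section 9.7.3), with no mention of death. Detailed methods and data conventions are left to a separate SAP, due before database lock (Sections 9 and 9.8), which is not among the documents supplied.

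Death is placed explicitly in only one graded outcome: "The ordinal scale of patient health status ranges from: 1) Death" (Section 8.2.2.3). All-cause mortality through Day 60 is a separate endpoint.

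**The concern.** A raw day count treats fewer days as better, but a patient can have few hospital days by going home or by dying. A patient who dies on Day 7 scores 7 hospital days; a survivor discharged on Day 14 scores 14. An arm with more early deaths can therefore appear to shorten the stay, and an arm that prevents early deaths can appear to lengthen it. Ranking the same counts does not remove the problem, and descriptive means carry it as well.

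The protocol also leaves a second reading open. If days after death were treated as missing, the multiple imputation in Section 9.7.3 would create hospital days for patients who are dead. The text neither requires nor excludes this.

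What is at stake is the initial assessment of clinical benefit, which Section 2.3 assigns to the secondary objectives while a larger trial is being prepared. The primary safety endpoint is not affected.

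**Working it through.** **Inputs.** From the documents: 40 patients randomized 1:1 (Section 9.3), so 20 per arm; counts run to Day 28; all randomized patients are analysed. The documents give no mortality, length of stay, support use or standard deviation, so every such figure below is an assumption. The plan has no figure of its own to reproduce.

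**Formula.** Let m be an arm's mortality by Day 28, d the mean counted days in patients who die, and s the mean in survivors, with d and s equal in both arms. If counting stops at death, the arm mean is (1 - m)s + m·d, so

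A - B = (mA - mB)(d - s).

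When A has the higher mortality, the sign depends only on whether d is below or above s.

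**Hospital days, s = 14, mortality 30% (A) v 15% (B).**
- d = 7: 0.70×14 + 0.30×7 = 11.90 v 0.85×14 + 0.15×7 = 12.95. A looks 1.05 days better.
- d = 14: 14.00 v 14.00. No shift.
- d = 21: 16.10 v 15.05. A looks 1.05 days worse.

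At 15% v 10% and d = 7 the shift is 0.05×(7 - 14) = -0.35 days. Over survivor stays of 10 to 14 days, deaths on Days 3 to 10 and 2 to 4 excess deaths among 20 in Arm A, it runs from 0.0 to -2.2 days.

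**Simulation.** 20,000 trials, 20 per arm; stay and death day lognormal (sigma 0.5, capped at 28), median stay 14.

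| Mortality A v B | Median death day | Mean A - B (days) | SE (days) | Mean rank favours A | t-test p<0.05 favouring A |
|---|---|---|---|---|---|
| 30% v 15% | 7 | -1.13 | 2.18 | 71% | 7.6% |
| 30% v 15% | 14 | 0.00 | 2.1 | 50% | 2.5% |
| 30% v 15% | 21 | +0.81 | 2.22 | 36% | 1.0% |
| 15% v 10% | 7 | about -0.4 | about 2.15 | 56 to 57% | about 3.5% |

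Chance alone gives about 2.5% in the last column.

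**Support days.** The qualifier *if applicable* can mean all patients, with never-users at 0, or users only. Take NIV/high flow at 30% v 15% mortality, with 20% of survivors using it for 6 days and every patient who dies using it for 3 days.
- All randomized: 0.70×0.2×6 + 0.30×3 = 1.74 v 0.85×0.2×6 + 0.15×3 = 1.47. A looks worse.
- Users only: 1.74/(0.14 + 0.30) = 3.95 v 1.47/(0.17 + 0.15) = 4.59. A looks better.

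The threshold for d moves from 0.2×6 = 1.2 days (all randomized) to 6 days (users only). For IMV/ECMO, with 10% of survivors on it for 8 days and every patient who dies on it for 4, the means are 1.76 v 1.28 in all randomized, and 1.76/0.37 = 4.76 v 1.28/0.235 = 5.45 in users. The sign reverses again.

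Oxygen follows the same formula. Over all randomized patients with s = 10, d = 7 gives 9.10 v 9.55 and d = 14 gives 11.20 v 10.60. A users-only reading raises s, and with it the range of d over which A looks better.

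**Same hospital inputs, days alive and out of hospital, death scored -1.** 0.70×(28 - 14) - 0.30 = 9.50 v 0.85×14 - 0.15 = 11.75, whatever the day of death. In the simulation the higher-mortality arm ranks behind in about 79% of trials at 30% v 15%. Scoring death as 0 instead would tie it with about 8% of survivors (2.6 per trial), those still in hospital at Day 28.

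**The case against.** **The SAP may already settle this.** A death rule for a day count is a data convention, and Section 9 assigns those to the SAP. This stands: a reader might infer that the trial has no rule, but the documents show only that the protocol is silent.

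**The direction is not fixed.** A reader might infer that the arm with more deaths always looks better. It does not. On hospital days this needs deaths earlier than typical discharge, and on the support counts it turns on the reading of *if applicable*. It also assumes that counting stops at death. Under imputation of days after death, the direction would depend on an imputation model that the protocol does not describe.

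**The effect is small, and mortality is visible.** A shift of 1.1 days or less against a standard error near 2.2 will seldom yield a nominally significant false benefit. The counts are four of many secondary endpoints in a trial sized by clinical judgment, and deaths are reported in the same list. All of this stands as a limit on severity. Reporting deaths alongside reveals an imbalance but does not correct the counts.

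**Other endpoints cover death.** This is true of the 8-point scale. It is tempting to say the same of "Difference in percentage of subjects with clinical recovery compared at Day 14 and Day 28", but Section 3 states no rule there for deaths, including a patient who meets recovery and then dies before the assessment day.

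**Conclusion.** The concern holds in a limited form. The protocol lists four raw counts as clinical benefit and states no rule for deaths. Counted literally over all randomized patients, hospital days credit early deaths as shorter stays. With a median stay of 14 days and median death on Day 7, the shift is about -1.1 days at 30% v 15% mortality and about -0.4 days at 15% v 10%. It vanishes with equal mortality or when deaths coincide with typical discharge, and reverses when deaths come later. For the support counts, the protocol does not determine the direction.

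These sizes rest wholly on assumed mortality, timing and support use, and on equal survivor stays in the two arms. This is a modest interpretability problem, worth fixing because the remedy is cheap.

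**What to change.** In the SAP, before outcome data are reviewed (the trial is open label, so waiting until just before database lock is late):

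- Analyse days alive and out of hospital, and days alive and free of supplemental oxygen, of NIV/high flow and of IMV/ECMO, through Day 28 in all randomized patients.
- Count survivors who never used a support as free of it throughout, which settles *if applicable*. A day on a higher level of support is not a free day for a lower one.
- Rank death by Day 28 below every survivor, for example with a score of -1.
- State that days after death are not missing and are not imputed.
- Use the rank-based method that Section 9.8.4.1 already allows, and report the raw counts descriptively beside mortality.

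**Cost.** The daily 8-point scale and the mortality record supply the in-hospital data. Oxygen after discharge needs its own record: category 7, "Not hospitalized, limitation on activities and/or requiring home oxygen", merges home oxygen with activity limitation, and the Schedule of Activities lists no separate item. The current oxygen count has the same need. The analysed measures become composites with mortality, and raw durations become descriptive. If the protocol's endpoint wording is changed to match, IRB approval is needed (Sections 11.2 and 12.1).

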5.1.1. Inclusion Criteria

Patients must meet all of the following inclusion criteria to be eligible for enrollment in the study:

- 1. Male or non-pregnant female adult ≥ 18 years of age
- 2. Diagnosed or confirmation of COVID-19 infection by standard RT-PCR assay or equivalent testing within 7 days prior to randomization (Day1).
- 3. Hospitalized patient with severe illness caused by SARS-CoV-2 (**Note:** Prior or current use of remdesivir or dexamethasone (SOC) are allowed under the investigator's discretion. Concomitant treatment with other investigational antiviral drugs or immunomodulators are not permitted from Day1 through Day 28)
 - Symptoms of severe systemic illness/infection with COVID-19:
 - At least 1 of the following: fever, cough, sore throat, malaise, headache, muscle pain, shortness of breath at rest or with exertion, confusion, or symptoms of severe lower respiratory infection including dyspnea at rest or respiratory distress

AND

- Clinical signs indicative of severe systemic illness/infection with COVID-19
 - At least 1 of the following: $RR \ge 30$, $HR \ge 125$, SaO2 < 93% on room air or requires $\ge 2L$ oxygen in order to normalize SaO2.
- 4. Patient (or legally authorized representative) provides written informed consent prior to initiation of any study procedures.
- 5. Adequate hematopoietic capacity, as defined by the following:
 - a. Hemoglobin \geq 9.0 g/dL and not transfusion dependent
 - b. Platelets $> 100,000/\text{mm}^3$
 - c. Absolute neutrophil count $\geq 1500 \text{ cells/mm}^3$

CONFIDENTIAL Page 27 of 66

- 6. Adequate hepatic function, as defined by the following:
 - a. AST and ALT ≤ 2.5 times upper limit of normal (ULN)
 - b. Total bilirubin $\leq 1.5 \text{ x ULN}$
 - c. Albumin $\geq 2.5 \text{ g/dL}$
- 7. Absence of any active or recurring clinically significant hepatic disease and adequate renal function, as defined by the following:
 - a. Renal: calculated creatinine clearance >45 mL/min for patients with abnormal, increased creatinine levels (Cockcroft-Gault formula).
- 8. Ability to take oral medication and be willing to adhere to drug administration and premedication requirements (see **Section 6.3**) throughout study duration.

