5.1.2. Exclusion Criteria

Potential subjects meeting any of the following criteria will be excluded from participation in this study:

- 1. Patient showing signs of respiratory failure necessitating mechanical ventilation
- 2. Pregnant or nursing women.
 - NOTE: Women of child-bearing potential and men must agree to use adequate contraception (hormonal or barrier method of birth control; or abstinence) prior to study entry and for the duration of study participation. Should a man father a child, or a woman become pregnant or suspect she is pregnant while participating in this study, he or she should inform the treating physician immediately.
- 3. Active or uncontrolled infections other than COVID-19 or with serious illnesses or medical conditions which would not permit the patient to receive study treatment
- 4. Active or planned concomitant treatment with other investigational antivirals or immunomodulators
- 5. Chronic diarrhea (excess of 2-3 stools/day above normal frequency)
- 6. Current use or anticipated need for drugs that are known strong inhibitors or inducers of major CYP enzymes.

CONFIDENTIAL Page 28 of 66

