9.7.1. Analysis Populations

9.7.1.1. Intent-to-Treat Population

The Intent-to-Treat (ITT) population is defined as all randomized subjects. This population will be used as the primary analysis population for analysis of the primary and secondary efficacy endpoints.

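### The count of patients returned to room air gives no credit for preventing oxygen need and can fall when deterioration is prevented; the support-day endpoints share the risk only if restricted to recipients

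*Combined protocol and SAP*

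**What the plan says.** The clinical-benefit objective in Section 3, repeated in the synopsis (Section 1.1), includes "Number of patients returned to room air after randomization through Day 14 or Day 28". No denominator, baseline oxygen condition, minimum duration or rule for death is attached. The symptom-based recovery endpoints in the same section, by contrast, require improvement lasting 48 hours.

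The same list contains three support-day endpoints: "Days of supplemental oxygen (if applicable) from randomization through Day 28", "Days of non-invasive ventilation/high flow oxygen (if applicable) from randomization through Day 28" and "Days of invasive mechanical ventilation/ECMO (if applicable) from randomization through Day 28". The qualifier in brackets is not defined anywhere. Days of hospitalization, in the same list, does not carry it.

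Three other parts of the protocol bear on how these endpoints behave:

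- **Entry.** Besides a symptom, inclusion criterion 3 (Section 5.1.1) asks for "At least 1 of the following: $RR \ge 30$, $HR \ge 125$, SaO2 < 93% on room air or requires" at least 2 L of oxygen to normalize saturation. One sign is enough, so oxygen use is not a condition of entry.
- **Exclusion.** Exclusion criterion 1 (Section 5.1.2) is "Patient showing signs of respiratory failure necessitating mechanical ventilation".
- **Population.** Section 9.7.1.1 states "The Intent-to-Treat (ITT) population is defined as all randomized subjects" and makes this the primary population for the secondary efficacy endpoints. Sections 9.8 and 9.8.4.1 leave endpoint-level detail to a separate SAP, due before database lock, which is not in the file.

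**The concern.** A patient who has never left room air cannot return to it. Because the entry criteria admit such patients, the count treats room-air entrants perversely: staying well scores nothing, while worsening and then being weaned scores a success. The count also runs through a day instead of describing status on that day, so a patient weaned on Day 5 who dies on Day 10 remains a success at Day 14 and at Day 28.

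The stated purpose is to judge clinical benefit relative to control. An effect the drug might well have, keeping patients off oxygen, is invisible on this endpoint and can push it the wrong way. The problem is one of direction, so it affects descriptive counts as much as any test.

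The support-day endpoints raise a related but weaker question. If the qualifier means that days are summarized only among patients who used the support, and use begins after randomization, the comparison conditions on something treatment can change.

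**Working it through.** The plan gives no figure to reproduce: Section 9.3 sets 40 patients, 1:1, by clinical judgment. The check is whether each endpoint can move against a drug whose only effect is to prevent support. Every rate below is an assumption, because the documents give none.

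**Room air, 20 per arm.** Let *r* be the number on room air at entry, *p* the share of them who later need oxygen, *w_b* = 0.70 the return rate of those on oxygen at entry (same in both arms), and *w_i* = 0.80 the return rate of those who start oxygen later. Deaths are ignored.

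- Counted as returned = *w_b*(20 − *r*) + *r p w_i*
- Actually on room air = *w_b*(20 − *r*) + *r*[(1 − *p*) + *p w_i*]

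Example, *r* = 6, *p* = 0.5 control and 0.1 drug. Returned: 0.70×14 + 6×0.5×0.80 = 12.20 against 0.70×14 + 6×0.1×0.80 = 10.28. On room air: 9.80 + 6×(0.5 + 0.40) = 15.20 against 9.80 + 6×(0.9 + 0.08) = 15.68.

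| *r* | *p* control / drug | Returned: control, drug | Drug − control | On room air: control, drug | Drug − control |
|---|---|---|---|---|---|
| 2 | 0.3 / 0.1 | 13.08, 12.76 | −0.32 | 14.48, 14.56 | +0.08 |
| 2 | 0.5 / 0.1 | 13.40, 12.76 | −0.64 | 14.40, 14.56 | +0.16 |
| 6 | 0.5 / 0.1 | 12.20, 10.28 | −1.92 | 15.20, 15.68 | +0.48 |
| 10 | 0.5 / 0.1 | 11.00, 7.80 | −3.20 | 16.00, 16.80 | +0.80 |

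The deficit equals *r w_i* × (difference in *p*), so it is proportional to the number entering on room air and vanishes at *r* = 0. To break even, the drug must raise the return rate of patients on oxygen at entry by deficit/(20 − *r*): 0.32/18 = 1.8 percentage points in the mildest row and 3.20/10 = 32 points in the most extreme. The latter would take 70% past 100%, so it cannot be reached.

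**Invasive ventilation days, 20 per arm, no deaths.** Suppose 6 controls are ventilated, 4 for 5 days and 2 for 20 days, a total of 60 days.

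- Control: 60/6 = 10.0 days among recipients; 60/20 = 3.0 over all randomized.
- Drug prevents one short course: 55/5 = 11.0 among recipients; 55/20 = 2.75 over all.
- Drug prevents all four short courses: 40/2 = 20.0 among recipients; 40/20 = 2.0 over all.
- Drug prevents one long course instead: 40/5 = 8.0 among recipients; 40/20 = 2.0 over all.

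The recipient-only mean reverses when the prevented courses are shorter than that mean, and does not when they are longer. The all-randomized mean has the right direction each time.

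**Oxygen days.** Suppose 14 per arm are on oxygen at entry for 10 days, and of 6 room-air entrants 3 controls and no drug patients need 4 days. Among recipients: control 152/17 = 8.9, drug 140/14 = 10.0. Over all randomized: control 152/20 = 7.6, drug 140/20 = 7.0.

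**Death.** Scoring never-supported patients as zero is not enough by itself: a patient who dies on Day 2 without ventilation would have zero ventilation days, the best possible score.

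**The case against.** The strongest reply concerns the support days. A reader might infer that the plan compares days only among recipients and so breaks the randomized comparison. The documents do not say that. Section 9.7.1.1 makes all randomized patients the primary efficacy population; if those never supported contribute zero days, the reversal disappears. The unseen SAP may say exactly this. Section 9.7 also requires n by arm, so even a recipient-only table would show that fewer drug patients were ventilated. All of this stands, with one limit: naming the population does not say what value a never-supported patient receives, and Section 9.7.3 plans multiple imputation for missing efficacy data, so a blank could be treated as missing.

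A reader might also infer that all support use begins after randomization. That is firm only for invasive ventilation/ECMO. The exclusion does not clearly cover non-invasive ventilation or high-flow oxygen, and needing oxygen is itself a route of entry.

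The consequence is limited too. Safety is primary, the sample size is unpowered, and Section 9.8.4 plans no inferential statistics (although Section 9.8.4.1 names models). The 8-point scale is collected daily to Day 28 and reported at Day 14 and Day 28 for every level, so the patient weaned and then dead appears there as a death; mortality to Day 60 is also reported. This is partial cover: level 7 combines limited activity with home oxygen, so the scale does not identify room-air status after discharge.

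Finally, the rates above are chosen to show direction. They are not estimates.

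**Conclusion.** The room-air point holds on the wording. The endpoint requires a return, entry does not require oxygen, and the count ignores what happens after weaning. Preventing deterioration earns no credit and can lower the count. Under the assumed rates the drug's deficit is 0.32 to 3.20 patients per arm of 20, while true room-air status favours it by 0.08 to 0.80. Those sizes depend on the share entering on room air, which is unknown, and on equal return rates in the two arms. If nearly all patients enter on oxygen, the effect is small.

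The support-day point is conditional: an undefined phrase that would mislead if read as restricting the comparison to recipients, most clearly for invasive ventilation/ECMO. It is not a demonstrated break of randomization. Nor do the documents support inferring that an effective drug will score worse. Reversal is possible, not expected, and depends on which courses are prevented.

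The rewording is worth making because Section 2.3 uses the secondary objectives for an initial assessment of clinical benefit. The primary safety objective is unaffected.

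**What to change.** In Sections 1.1 and 3:

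- Replace the room-air endpoint by *percentage of all randomized patients alive and breathing room air on Day 14 and on Day 28*. The same percentage among those on oxygen on Day 1 can be added as a secondary summary.
- Record current oxygen use as its own item at the daily remote contacts after discharge, since level 7 of the scale cannot supply it.
- Remove the bracketed qualifier from the three support-day endpoints and define them over all randomized patients with an explicit rule for death: for example, days alive and free of that support to Day 28, with 0 assigned to anyone who dies by Day 28.
- Report, per arm, the number who ever needed each type of support.

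No visits are added. The costs are an amendment to the wording, one extra item at remote contacts, and skewed data with many ties, which the rank-based methods already named in Section 9.8.4.1 can accommodate. The definitions belong in the protocol: the trial is open-label and the SAP need only be approved before database lock, so a later choice of denominator could be made with outcomes in view.
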